### **10.3 Relevant CIP deviations**

All CIP deviations will be listed in the study report.

No deviations from the CIP and of any type will be made without complying with all IRB/EC established procedures in accordance with applicable regulations.

### **10.4 Statistical analysis plan**

The statistical analysis plan will be elaborated by the Principal Investigator together with a statistician.

### **10.5 Missing, unused and spurious data**

Plausibility Checks will be performed regularly, missing data will be treated by the last observation carried forward principle.

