#### **Follow-up of patients withdrawn from the clinical investigation**

In case of premature discontinuation after treatment with the medical device , the investigations scheduled for the EOS visit will be performed **7** days after discontinuation. The subjects will be advised that participation in these investigations is voluntary. Furthermore, they may request that from the time point of withdrawal no more data will be recorded and that all biological samples collected in the course of the clinical investigation will be destroyed.

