**7.6.2 Screening investigation**

**BEFORE TREATMENT RANDOMISATION V-1**

*(Study Day 1)*

After signing the informed consent all patients will be screened according to exclusion and inclusion criteria. Patients will be investigated as follows:

- Prior medical history will be assessed.
- ECG (Electrocardiogram) will be performed
- blood pressure
- blood samples will be collected ( TNF $\alpha$ , IL6, CRP and NT-proBNP levels will be assessed).
- base line LVEF (not older than 14 days) assessed by transthoracal echocardiography
- 6 min walk test
- quality of life assessment with SF 36
- Assessment of NYHA classification (see table 2)

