#### V1-V4

(Study Day 14, 21, 28, 35)

Patients receive new device, possible adverse events can be assessed, possible complications/questions can be discussed.

Day 21: 6 minutes walk test will be performed again.

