#### End of Study Visit V5

(Study Day 63)

- ECG (Electrocardiogram) will be performed
- blood pressure
- blood samples will be collected ( TNF $\alpha$ , IL6, CRP and NT-proBNP levels will be assessed).
- LVEF (not older than 14 days) assessed by transthoracal echocardiography
- 6 min walk test
- quality of life assessment with SF 36
- Assessment of NYHA classification

Class	Patient Symptoms
Class I (Mild)	No limitation of physical activity. Ordinary physical activity does not cause undue fatigue, palpitation, or dyspnea (shortness of breath).
Class II (Mild)	Slight limitation of physical activity. Comfortable at rest, but ordinary physical activity results in fatigue, palpitation, or dyspnea.
Class III (Moderate)	Marked limitation of physical activity. Comfortable at rest, but less than ordinary activity causes fatigue, palpitation, or dyspnea.
Class IV (Severe)	Unable to carry out any physical activity without discomfort. Symptoms of cardiac insufficiency at rest. If any physical activity is undertaken, discomfort is increased.

Table 2: New York Heart Association (NYHA) Classification

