#### **Intention to treat set**

This analysis set includes subjects who were randomized and received at least one dose medical device Main analysis is by the intention-to-treat principle. Here, an outcome value is necessary for each patient, if a patient drops out. Therefore, we will use the interim assessment of walking distance after 2 weeks of treatment, or, if this is unavailable, the baseline measurement (i.e., the patient is counted as a non-responder to treatment) as replacement in such cases.

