### **10.6 Endpoints analysis**

The primary end point (walking distance in 6 minutes) will be analysed by analysis of covariance, taking the baseline value as covariate into account, and the treatment group as factor.

Continuous secondary outcome variables will be analysed by analysis of covariance as described above. Change in NYHA classification will be described by contingency tables, and the percentage of patients with an improvement in NYHA will be compared using a Fisher's exact test.

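### For LVEF, SF-36, NYHA class and the biomarkers, last observation carried forward enters zero change for any dropout without an early end-of-study assessment, and this biases the treatment comparison

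*Combined protocol and SAP*

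**What the plan says.** The general missing-data rule is in Section 10.5: "missing data will be treated by the last observation carried forward principle". It names no endpoint and no exception. Section 10.1 (Intention to treat set) adds a rule for walking distance only: "we will use the interim assessment of walking distance after 2 weeks of treatment, or, if this is unavailable, the baseline measurement". There the plan says openly that falling back on baseline treats the patient as a non-responder. It offers no such reasoning for any other outcome.

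The visit schedule in Section 7.6.2 determines what can be carried forward. At V-1 (Day 1) the biomarkers (TNF-alpha, IL-6, CRP, NT-proBNP), the walk test, SF-36, NYHA class and LVEF are recorded, the last as "base line LVEF (not older than 14 days) assessed by transthoracal echocardiography". At V1 to V4 (Days 14 to 35), "Patients receive new device, possible adverse events can be assessed, possible complications/questions can be discussed", and the one efficacy measurement is this: "Day 21: 6 minutes walk test will be performed again". At V5 (Day 63) the full set returns, including "quality of life assessment with SF 36".

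Patients who stop early are covered in two places. Under Section 6.1.5, "the investigations scheduled for the EOS visit will be performed" 7 days after discontinuation, and attendance is voluntary. The two paragraphs on premature permanent discontinuation that follow Section 7.2.3 place the assessments before the device is discontinued, where possible.

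On analysis, Section 10.6 says: "Continuous secondary outcome variables will be analysed by analysis of covariance as described above". That means baseline as covariate and treatment as factor. NYHA improvement is compared by Fisher's exact test. No sensitivity analysis for missing data is named.

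**The concern.** LOCF needs an intermediate value to carry. Walking distance has one, on Day 21. LVEF, SF-36, NYHA class and the biomarkers have none, so for a dropout not seen at an early end-of-study assessment the rule copies baseline into the final column. The ANCOVA then treats that copy as a measured outcome, with the same baseline value as covariate.

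Three things are at stake:

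- The estimated difference is biased, in a direction that depends on how dropout falls between the arms.
- For continuous outcomes, patients with no final measurement count towards precision.
- For NYHA, a patient whose final class is unknown is recorded as not improved.

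This is a pilot, so its secondary effect estimates and SDs are likely to feed the design of a later trial.

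**Working it through.** **The plan's own figure.** Section 10.2 assumes a difference of 30 m and an SD of change of 30 m, with two-sided alpha 0.05. The two-group t-test has 78.1% power at 16 per group and 80.7% at 17, so 17 is reproduced. Going from 17 to 20 implies dropout of 1 - 17/20 = 15%, that is, 3 of 20 per arm. The plan states no rate. It gives no effect, SD or correlation for the secondary outcomes, so everything below on those points is an assumption.

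**Expected value under baseline carried forward.** Let d1 and d0 be the fractions carried forward in the verum and placebo arms, m the mean change on placebo and e the true effect. If dropout is unrelated to outcome within an arm:

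expected LOCF difference = (1 - d1)(m + e) - (1 - d0)m = (1 - d1)e - (d1 - d0)m

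- Equal dropout, 3 of 20 per arm, e = 0.8: 0.85 x 0.8 = 0.68 (-15%).
- The same, with half the dropouts attending early and their value taken as equal to Day 63: 0.925 x 0.8 = 0.74 (-7.5%).
- No effect, m = 0.5, 5 v 1 missing: -(0.25 - 0.05) x 0.5 = -0.10. With 1 v 5 missing: +0.10. With half attending, 5 v 1 gives -0.05.
- No effect, m = 0, 5 v 1 missing: no bias.
- Inflation is possible: changes of 1.0 and 0.5 with 10% v 30% dropout give 0.9 x 1.0 - 0.7 x 0.5 = 0.55 against a true 0.50.

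**Simulation of the planned ANCOVA.** 20 per arm, outcome SD 1, baseline-to-final correlation 0.7, 6,000 trials per scenario, no early assessments:

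| Scenario | LOCF | Observed values only |
|---|---|---|
| Effect 0.8, no common change, 3 v 3 missing | 0.68, SE 0.222, coverage 92.9%, power 86% | 0.80, SE 0.246, coverage 94.6%, power 88% |
| Effect 0.8, common change 0.5, 3 v 3 missing | 0.68, SE 0.241, coverage 94.8%, power 81% | 0.80, SE 0.246, power 87% |
| No effect, common change 0.5, 5 v 1 missing | -0.10, rejection about 6.7% | 0.00, rejection about 5% |

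The SE gap is 1 - 0.222/0.246 = 10% in the first row and 1 - 0.241/0.246 = 2% in the second. With all 40 patients measured the SE would be 0.227. In the first row, therefore, LOCF with six patients missing reports slightly more precision than complete data.

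A second set of assumptions agrees: SD of change 1, correlation 0.75, effect 1, 15% equal dropout. LOCF gives 0.85, SE 0.288 and coverage 92.0%. Observed values give 1.00, SE 0.324 and coverage 95.2%. At 5% dropout the LOCF estimate is 0.95; at 30% it is 0.69.

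**NYHA.** A carried-forward patient cannot have improved. With assumed improvement of 50% v 20% and 15% dropout in each arm, the table shows 0.85 x 50 = 42.5% v 0.85 x 20 = 17%, a difference of 25.5 points instead of 30. With 50% in both arms and dropout of 10% v 30%, it shows 45% v 35%, a false difference of 10 points.

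**The case against.** The strongest reply is that the plan does provide for patients who stop early. The end-of-study list includes LVEF, SF-36, NYHA and bloods, so a dropout who attends has a post-baseline value to carry. This stands. A reader of the visit table alone might infer that baseline is always the only value available, and the documents do not support that. But attendance is voluntary or conditional, no attendance rate is assumed, and half attendance halves the bias without removing it.

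A reader might also infer that LOCF always shrinks effects and is therefore conservative. That holds for equal dropout at random. With unequal dropout the same rule can create or inflate a difference.

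Third, it is tempting to say that the standard errors are wrong and the tests invalid. They are not too small for the LOCF estimator itself: in the first simulated scenario the model SE is 0.222 and the empirical SD of the estimate about 0.214. The lower coverage there comes from the shift in the estimate. With equal dropout and no effect, rejection stays at 4 to 5%. What can be said is narrower: the SE is below what the observed data support, and by only 2% when both arms improve by 0.5 SD. The SE argument does not apply to NYHA, which is compared by Fisher's exact test.

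Finally, these are secondary endpoints of a 40-patient pilot, and Section 10.4 leaves a fuller analysis plan to be written. That limits the weight of the point, but Section 10.4 does not withdraw the rule in Section 10.5.

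**Conclusion.** The point holds in this form. For LVEF, SF-36, NYHA class and the biomarkers, the LOCF rule enters zero change for every dropout without an early end-of-study assessment. At the dropout implied by the sample size, the bias is about 7 to 15% towards zero if the arms lose patients equally. It is about 0.10 SD in either direction under no effect if 5 v 1 patients are missing and both arms change by 0.5 SD. The power of the LOCF analysis is no higher than that of observed-value ANCOVA (81 to 86% v 87 to 88%), so filling in values gains nothing.

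These sizes rest on the assumed correlation, effects and dropout, on dropout unrelated to outcome within arm, and on early values equal to Day 63 values where attendance is modelled. The mechanism itself needs only the visit schedule and Section 10.5. The effect is modest and does not threaten the primary analysis, which has its own rule and a Day 21 value. The rule should be changed because a better one is available at little cost.

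**What to change.** - **Section 10.5:** for the continuous secondary outcomes, replace LOCF by ANCOVA on the observed end-of-study values, or by multiple imputation within arm from baseline variables. Keep LOCF as a labelled sensitivity analysis.
- **NYHA (Section 10.6):** show missing as a separate row of the contingency table, and state which denominator Fisher's test uses.
- **Section 10.1:** say that single-value replacement applies to walking distance only, since the text there requires an outcome value for every patient who drops out.
- **Early end-of-study assessment:** Section 6.1.5 and the discontinuation paragraphs after Section 7.2.3 differ on timing (7 days after stopping, or before the device is discontinued). They must be reconciled, and the plan should say how these values enter the analysis.

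The cost is a few sentences, about 34 analysed patients instead of 40 at 15% dropout (40 x 0.85), and slightly wider intervals. Observed-value ANCOVA is valid only if missingness depends on baseline and arm alone. The documents cannot establish this, which is why a sensitivity analysis should stay in the plan.

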### **10.6 Endpoints analysis**

The primary end point (walking distance in 6 minutes) will be analysed by analysis of covariance, taking the baseline value as covariate into account, and the treatment group as factor.

Continuous secondary outcome variables will be analysed by analysis of covariance as described above. Change in NYHA classification will be described by contingency tables, and the percentage of patients with an improvement in NYHA will be compared using a Fisher's exact test.

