## 2. SYNOPSIS OF THE CLINICAL INVESTIGATION

TITLE	Clinical Outcome of Electrical Auricular Vagal Stimulation in Patients with Stable Symptomatic Chronic Heart Failure -a Pilot Study					
ACRONYM	(abbreviated title)					
NAME OF DEVICE	Dev1					
DESCRIPTION OF THE PROCEDURES	P-Stim® is an investigational device intended to deliver electrical auricular acupuncture in individuals suffering from heart failure. The device system is to be used only in accordance with the approved Investigational Plan on subjects who have signed an informed consent form. Device use is limited to the approved study investigators.					
OBJECTIVES	
In this study the effects of electrical auricular acupuncture on symptomatic chronic heart failure will be assessed.
 
Primary Objective:
 

- Six-minute walk test

 
Secondary Objective:
 

- Left ventricular ejection fraction (LVEF)

- New York Heart Association (NYHA) classification

- In addition the patient's quality of life (regarding to different areas in daily life, mobility etc.) will be assessed by a quality of life questionnaire (SF 36)

- Adverse events of acupuncture will be recorded

- Inflammatory cytokines TNF <math>\alpha</math>, IL6, NT-proBNP, CRP, will be collected to measure a possible influence of electrical auricular acupuncture on inflammation

- Ventricular and/or atrial arrhythmia documented in a subgroup of patients with implanted cardiac rhythm management devices.

					
TYPE OF THE INVESTIGATION	Prospective, single center, randomized, parallel group, double-blind, placebo-controlled					
PERIOD OF ENROLMENT	First patient First visit	1.1.20 13	Last patient First visit	31.12. 2013	Last patient Last visit	28.2.10 14
CENTER(S) / COUNTRY(IES)	1 center, Medical University Vienna, Austria					
PATIENTS / GROUPS	40 patients in 2 groups 20 patients per group Randomization ratio 1:1, stratification gender					
INCLUSION CRITERIA	

- Stable symptomatic chronic heart failure, defined by:

- NYHA Classification II-III

- Optimal medical treatment (ESC guidelines 2012) for at least 1 month

					

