	
 
- LVEF <40%
 
- Patients must be able to understand study conditions
 
- No exclusion criteria
 
- Signed informed consent
 

EXCLUSION CRITERIA	
 
- Ventricular tachyarrhythmia within 1 month prior to base line visit
 
- Any electrical auricular vagal stimulation treatment within 6 months prior to base line visit
 
- Participation in another clinical trial within 3 months prior to base line visit
 
- Psoriasis vulgaris
 
- Hemophilia
 
- Cardiac pace makers
 

COMPARATIVE DEVICE	Placebo
CONCOMITANT MEDICATION/CON-COMITANT DEVICE	Not applicable
EFFICACY ENDPOINTS	Clinical outcome of heart failure definition see above
TOLERABILITY / SAFETY ENDPOINTS	Adverse Events will be recorded
QUALITY OF LIFE	SF 36 questionnaire
STATISTICAL METHODOLOGY	
 
• Primary Endpoint 6 minute walk test
 
• Null and alternative hypotheses: <math>H_0</math>: electrical auricular vagal stimulation does not increase 6min walk test <math>H_1</math>: electrical auricular vagal stimulation increases 6min walk test
 
• Type-I and -II errors - power. <math>\alpha</math> 0.05 (two sided) <math>\beta</math> 0.20 (Power =80%)
 
• Interim analysis
 
• Statistical methodology The primary end point (walking distance in 6 minutes) will be analysed by analysis of covariance, taking the baseline value as covariate into account, and the treatment group as factor.
 
• Continuous secondary outcome variables will be analysed by analysis of covariance as described above. Change in NYHA classification will be described by contingency tables, and the percentage of patients with an improvement in NYHA will be compared using a Fisher's exact test.
 
• Sample size calculation. We assume a clinically relevant difference in the improvement in walking distance of 30 meters comparing the electrically stimulated
 

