#### **7.3 Randomization and stratification:**

After the screening visit, patients will be randomized into one of the following treatment groups: group V (Verum electrical vagus stimulation) or group P (placebo).

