**Unblinding -procedure at the end of the clinical investigation:**

At the end of study, codes will be unblinded and data will be analyzed.

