### **10.2 Sample size considerations**

We assume a clinically relevant difference in the improvement in walking distance of 30 meters comparing the electrically stimulated acupuncture group to the Placebo group. Furthermore, we assume a standard deviation in the improvement of the walking distance of 30 meters (Kirsten 2010).

A sample size of 17 in each group will have 80% power to detect this clinically relevant difference between the groups using a two group t-test with a 0,050 two-sided significance level. Because of the possibility of drop-outs we include 2x20 patients.

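### The synopsis stratifies randomisation by gender but the ANCOVA omits gender; if the arms are balanced on gender and it predicts outcome beyond baseline, reported standard errors are too large

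*Combined protocol and SAP*

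**What the plan says.** The synopsis (section 2, patients and groups) sets the allocation as "Randomization ratio 1:1, stratification gender". Section 7.3, whose heading covers both randomisation and stratification, says only that "patients will be randomized into one of the following treatment groups". It names no stratification factor and no blocking method.

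Section 10.6 analyses the primary endpoint by "analysis of covariance, taking the baseline value as covariate into account, and the treatment group as factor". The synopsis gives the same model: "taking the baseline value as covariate into account, and the treatment group as factor". Section 10.6 then applies this model to the continuous secondary outcomes. Gender appears in no analysis text.

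Section 10.4 defers further detail: "The statistical analysis plan will be elaborated by the Principal Investigator together with a statistician". It makes no commitment on covariates.

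**The concern.** When the arms are balanced on a prognostic factor, that factor no longer contributes to the true variability of the treatment estimate. If the analysis model leaves the factor out, its contribution stays in the residual variance. The reported standard error then overstates the real uncertainty, confidence intervals are too wide and the test rejects less often than its nominal 5%.

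The stake is efficiency and honest reporting of precision, not validity. In a 40-patient pilot the interval is one of the main products, so needless width is worth avoiding. There is also a plain textual gap: a reader of section 7.3 cannot tell whether, or on what, the allocation is stratified.

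**Working it through.** **The plan's own figure.** Section 10.2 gives a 30 m difference, a 30 m SD, two-sided 5%, 80% power and 17 per group. The normal approximation gives 2 × (1.960 + 0.842)² × (30/30)² = 15.7, so 16. With the exact noncentral t, power is 78.1% at 16 and 80.7% at 17 per group. The stated 17 is therefore reproduced. At 20 per group the t-test has 86.9% power.

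**Inputs for the check**

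- From the plan: 20 per arm, 30 m effect, two-sided 5%, and the ANCOVA of section 10.6.
- From the plan, but reinterpreted: section 10.2 says "we assume a standard deviation in the improvement of the walking distance of 30 meters". Here 30 m is used as the total SD S left after baseline adjustment. The true ANCOVA residual SD may be smaller, so 25 m is also run.
- Assumed: share of women p = 0.30, and gender difference at equal baseline d = 0, 15 or 30 m. The last equals the whole planned treatment effect.

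**Closed form.** Holding the total SD at S, the within-gender SD is √(S² − p(1 − p)d²).

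- d = 15 m: √(900 − 0.21 × 225) = √852.75 = 29.2 m.
- d = 30 m: √(900 − 0.21 × 900) = √711 = 26.7 m.

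With balanced arms, the model without gender works with about 30 m while the estimate varies as if the SD were 29.2 or 26.7 m. The reported standard error is too large by a factor of about 30/29.2 = 1.03 or 30/26.7 = 1.12.

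**Simulation, balanced arms** (6 women and 14 men per arm, complete data, S = 30 m, 200,000 replicates). Each cell shows the model without gender, then with gender.

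| | d = 0 m | d = 15 m | d = 30 m |
|---|---|---|---|
| True SD of estimate (m) | 9.6 / 9.6 | 9.4 / 9.4 | 8.5 / 8.5 |
| Mean reported SE (m) | 9.6 / 9.6 | 9.6 / 9.3 | 9.6 / 8.5 |
| Mean 95% CI width (m) | 38.7 / 38.8 | 38.8 / 37.7 | 38.9 / 34.4 |
| CI coverage (%) | 95.0 / 95.0 | 95.6 / 95.0 | 97.3 / 95.1 |
| Type I error (%) | 5.0 / 5.0 | 4.4 / 5.0 | 2.8 / 5.0 |
| Power (%) | 86 / 86 | 86 / 88 | 88 / 93 |

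The mean estimate was 30.00 to 30.02 m for a true 30 m, so there is no bias. The first two rows carry the point: the true variability is the same under both models, and only the reported error differs. Rounding exaggerates the power gain at 15 m. A separate run of 60,000 replicates gives 86.8% against 88.0%, a gain of 1.2 points.

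**Smaller SD.** With S = 25 m (100,000 replicates), type I error without gender is 5.0, 4.2 and 1.9%. Power is 95 / 95, 96 / 97 and 98 / 99%.

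**Share of women.** Runs with permuted blocks of 4 within gender (S = 30 m, 40,000 replicates) used 20% and 50% women. At a 20 m difference, type I error without gender is 4.1% and 4.0%. At 30 m it is 3.3% and 2.6%. Adding gender gives 4.8 to 5.1% in these cases.

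**Stratification not carried out** (S = 30 m, 100,000 replicates). Type I error is about 5% under either model. Power is 86 / 85, 86 / 87 and 86 / 92% for d = 0, 15 and 30 m. The true SD of the estimate is 9.6 / 9.8, 9.6 / 9.5 and 9.7 / 8.7 m. Here the reported errors are correct, but real precision is forgone when gender matters.

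**The case against.** The strongest reply is that the consequence needs two conditions the documents do not secure.

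- **Stratification must actually balance the arms.** The only evidence for it is a short entry in the synopsis. Section 7.3, the operative text, gives no factor and no blocks, and without stratification the conservatism disappears. This stands, and the conclusion is conditional on it.
- **Gender must matter beyond baseline walking distance.** The covariate already absorbs whatever part of the gender effect baseline carries. At a 10 m residual difference and 30% women, type I error is 4.6% against 4.9% and power 86.2% against 86.7%, which is negligible. The clearly visible loss needs a gender gap as large as the planned treatment effect. This also stands.

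The direction is harmless as well: a slightly conservative test in a pilot cannot create a false claim of benefit. And section 10.4 leaves room for a fuller analysis plan that could still add gender. That lowers the urgency, but the synopsis and section 10.6 already state a definite model, and nothing in the documents changes it.

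**Conclusion.** The point holds as a low-severity improvement. Two facts are certain: gender is the stratification factor in the synopsis but is in no analysis model, and section 7.3 does not name it.

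The numerical consequence is conditional. With arms balanced on gender and a residual gender effect of 0 to 15 m, the loss is nil to about 1 point of power, and type I error falls no lower than 4.4% (4.2% if the SD is 25 m). At 30 m, type I error is 2.8% and the loss is about 4 to 5 points of power. These figures assume 30% women, a 30 m SD after baseline adjustment unless stated, and complete outcomes.

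Only the walking-distance scale was simulated. For LVEF, SF-36 and the biomarkers the direction is the same under the same conditions, but the size is unknown. There is no bias, no inflation of false positives and no reason to change the sample size.

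**What to change.** Add gender as a fixed factor to the primary ANCOVA and the continuous secondary ANCOVAs, in the synopsis and section 10.6 or in the analysis plan that section 10.4 announces. Do this before the codes are opened; section 7.4 places that step at the end: "At the end of study, codes will be unblinded and data will be analyzed". Fixing the model beforehand also rules out a later choice between adjusted and unadjusted results.

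In section 7.3, name gender as the stratification factor so that it agrees with the synopsis, and state how balance within gender is obtained.

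The cost is one line of wording in each place and one residual degree of freedom (40 − 3 = 37 becomes 40 − 4 = 36), with no new data. If gender has no effect, power is unchanged with balanced arms (85.9% either way). It falls by 1 point if stratification is not carried out (85.8% to 84.8%).
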